8.1 Efficacy Assessments

8.1.1 Primary Efficacy Assessment – Gastric Emptying Breath Test

The GEBT is a nonradioactive noninvasive test that measures gastric emptying. Patients will provide baseline (premeal) breath samples and then consume a standardized 230 kCal meal, consisting of a proprietary standardized ¹³C labeled egg component (which is rehydrated and then microwaved for 1.5 minutes) and 6 saltine crackers, accompanied by 6 ounces of water. The meal is to be consumed within 10 minutes. Single post meal breath samples are collected in capped glass tubes at 45, 90, 120, 150, 180, and 240 minutes after the meal is consumed and sent to the specified local laboratory for analysis by Gas Isotope Ratio Mass Spectrometry. By adding ¹³C to the test meal, the GEBT can determine how fast the stomach empties the meal by measuring the rate of carbon-13 dioxide (¹³CO2) excretion arising from the digested test meal.

The GEBT measures the rate of ¹³CO₂ excretion after consumption of a ¹³C-enriched test meal. As the ¹³C enriched meal is emptied from the stomach it is digested, assimilated and ¹³CO₂ is excreted in the breath. At any given measurement time t, the ¹³CO₂ excretion rate is related to the rate of gastric emptying. A larger kPCD value means a faster ¹³CO₂ excretion rate which is proportional to a faster rate of gastric emptying.

Version 3.0 45 of 85 20 April 2022

In subjects with normal gastric emptying, ¹³CO2 excretion rates obtained by GEBT generally rise to a maximum between 120 and 180 minutes and then start to decrease because nearly all of the of the ¹³C-labeled test meal has been emptied from the stomach. In subjects with delayed emptying, ¹³CO2 excretion rates likewise start to rise after ingestion of the meal, but rates are lower and rarely reach a maximum before the end of the evaluation period (240 minutes) as a significant portion of the meal remains in the stomach and digestion and assimilation are incomplete.

Planned timepoints for all efficacy assessments are provided in the SoA (Table 1).

8.1.2 Secondary Efficacy Assessment – ANMS GCSI-DD

The ANMS GCSI-DD is designed to assess gastrointestinal symptoms associated with IG and DG. The ANMS GCSI-DD symptom assessments are based on a 24-hour recall period to minimize bias in patient recall. The instrument asks patients to rate the severity of five symptoms: bloating (feeling like you need to loosen your clothes), nausea, not able to finish a normal-sized meal, feeling excessively full after meals, and upper abdominal pain. The severity response is rated by the patient as the worst severity of the symptom over the previous 24 hours. The severity of symptom response scale ranges from 0 ("none"), 1 ("mild"), 2 ("moderate"), 3 ("severe") to 4 ("very severe"). In the scoring of vomiting episodes, the number of episodes of vomiting per day is used, with the episodes capped at 4, so that the scoring is similar to the symptom severity scores of the other items. Therefore, vomiting episodes are scored as 0=none; 1=one episode; 2=two episodes; 3= three episodes and 4= four or more episodes.

The ANMS GCSI-DD total gastroparesis symptom daily score is generated by summing the scores on each of the five symptom items and then dividing by 5, that is the number of items within the gastroparesis related symptom score. Thus, the maximum total symptom score could be (5 symptoms * maximum score 4 divided by 5); hence, the maximum score is 20/5=4. The ANMS GCSI-DD gastroparesis symptom daily score can range from 0 to 4. High scores on the ANMS GCSI-DD reflect greater symptom severity. The minimum clinically important difference in the ANMS GCSI-DD score has been estimated to be 0.50.

In addition, overall severity of gastroparesis is assessed. The overall severity of gastroparesis takes into account that other symptoms might impact on a patient's condition.

In this study, the change from baseline over time for the ANMS-GCSI-DD score will be assessed by comparing the following:

Change from baseline in the ANMS GCSI-DD) (i.e. Day-7 to Day -1) (predose) and Day 7 (Day 1 to Day 7)

Version 3.0 46 of 85 20 April 2022

Change from baseline in the ANMS GCSI-DD (i.e., Day-7 to Day -1) (predose) and Day 14 (Day 8 to Day 14)

Change from baseline in the ANMS GCSI-DD (i.e., Day-7 to Day -1) (predose) and Day 21 (Day 15 to Day 21)

Change from baseline in the ANMS GCSI-DD (i.e., Day-7 to Day -1) (predose) and Day 28 (Day 22 to Day 28)

The ANMS-GCSI-DD sub scores will also be assessed as an Exploratory Endpoint:

Change from baseline in the sub scores (nausea, early satiety, postprandial fullness, upper abdominal pain and number of vomiting episodes) of the ANMS-GCSI-DD over time (Day 7, 14, 21, 28) by comparing Day 7 to Day 14, Day 14 to Day 21 and Day 21 to Day 28.

The patients will complete these assessments using an electronic diary.

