The GEBT at Visit 2 and Visit 6 will be performed at the sites. Patients will be told to fast overnight prior to coming to the site for the test. The patient will have their glucose tested via fingerstick both before and after the GEBT. The patient must have a fasting blood glucose (FBG) of \leq 275 mg/dL to proceed with the GEBT. If the patient does not have a FBG of \leq 275 mg/dL prior to the GEBT, the patient may come in the following day to take the GEBT. The GEBT is a nonradioactive, noninvasive test that measures gastric emptying. Patients provide baseline (premeal) breath samples and then consume a standardized 230 kCal (kilocalorie) meal, consisting of a proprietary standardized ¹³C labeled egg component (which is rehydrated and then microwaved for 1.5 minutes) and 6 saltine crackers, accompanied by 6 ounces of water. The meal is to be consumed within 10 minutes. Single post meal breath samples are collected in capped glass tubes at 45, 90, 120, 150, 180, and 240 minutes after the meal is consumed and sent to the specified local laboratory for analysis by Gas Isotope Ratio Mass Spectrometry. By adding ¹³C to the test meal, the GEBT can determine how fast the stomach empties the meal by measuring the rate of carbon-13 dioxide (¹³CO₂) excretion arising from the digested test meal. The rate of ¹³CO₂ excretion found in the patient's breath is proportional to the patient's rate of gastric emptying.

The total study duration for each patient will be approximately 8 weeks.

Number of patients (planned):

Total number randomized into this study: 24 patients with moderate to severe gastroparesis who have documented delayed gastric emptying. The randomization to treatment groups will be stratified by type (IG, DG), enrolling at least 2 patients of each type in each treatment group.

Diagnosis and Main criteria for Eligibility:

Inclusion criteria:

- 1. Has a documented diagnosis of moderate to severe IG or DG according to the ANMS GCSI-DD score during the Screening Period (Score of > 2 on average of the screening days).
- 2. Moderate to severe delay in gastric emptying rate as measured by GEBT at Screening defined as GE half-time (t1/2) ≥ the 80th percentile of normative data as determined by Cairn Diagnostics.
- 3. Male or female patients 18 to 80 years of age, inclusive, at baseline.

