- Change from baseline in the ANMS GCSI-DD (i.e., Day-7 to Day -1) (predose) and Day 21 (Day 15 to Day 21).
- Change from baseline in the ANMS GCSI-DD (i.e., Day-7 to Day -1) (predose) and Day 28 (Day 22 to Day 28).

Exploratory Endpoints

- Change from baseline in ANMS GCSI-DD score over time (Day 7, 14, 21, 28) by comparing Day 7 to Day 14, Day 14 to Day 21 and Day 21 to Day 28.
- Change from baseline in the subscores (nausea, early satiety, postprandial fullness, upper abdominal pain and number of vomiting episodes) of the ANMS-GCSI-DD over time (Day 7, 14, 21, 28) by comparing Day 7 to Day 14, Day 14 to Day 21 and Day 21 to Day 28.
- Change from baseline in PAGI-SYM and PAGI-QOL scores over time by comparing Day 1 to Day 28.
- Change from baseline in Clinical Global Impression-Severity (CGI-S) and Clinical Global Impression-Improvement (CGI-I) scores over time by comparing Day 1 to Day 28.
- Change from baseline in PGI-S and PGI-C scores over time by comparing Day 1 to Day 28.

Safety Endpoints

- Adverse Events (AEs) (by type, severity, and relatedness) at each visit.
- Changes in safety clinical laboratory testing and vital signs at each site visit.
- Changes in ECGs at each site visit and the potential correlation of the PK with changes in the ECG.
- Change from baseline in the C-SSRS scores over time by comparing Day 1 to Day 28.

STATISTICAL ANALYSES:

Analysis Sets:

- Safety Set: All patients enrolled in the study who received at least 1 dose of treatment.
- PK Analysis Population: Patients in the Safety Set with at least 1 plasma sample with a quantifiable concentration of PCS12852.

Version 3.0 13 of 85 20 April 2022

Name of Investigational Product: PCS12852

Name of Active Ingredient: PCS12852

• Full Analysis Set (FAS): All patients who are randomized.

Other populations (e.g., Per Protocol) may be defined and used as supportive evidence of treatment benefit.

Patient Characteristics:

Baseline demographics and disease characteristics will be presented for each treatment group by descriptive statistics. All descriptive summary statistics of continuous variables will include n, mean, median, standard deviation (SD), minimum and maximum. All descriptive summaries presenting frequencies and incidences will include n, percent of total, and N, where N is the total number of patients with recorded values in the corresponding group. Patient completion status and exposure outcomes will be similarly presented.

Primary Efficacy Analyses:

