5.1 Inclusion Criteria

Patients are eligible to be included in the study only if all of the following criteria apply:

- 1. Has a documented diagnosis of moderate to severe DG or IG according to the ANMS GCSI-DD score during the Screening period (Score of >2 on average of the screening days).
- 2. Moderate to severe delay in gastric emptying rate as measured by the GEBT at Screening defined as GE half-time (t1/2) ≥ the 80th percentile of normative data as determined by Cairn Diagnostics.
- 3. Male or female patients 18 to 80 years of age, inclusive, at baseline.
- 4. Has continuous moderate to severe symptoms for gastroparesis (that is, chronic postprandial fullness, abdominal pain, postprandial nausea, vomiting, loss of appetite and/or early satiety) as assessed by the investigator for at least the past 3 months.
- 5. Has hemoglobin A1c (HbA1c) less than (<) 11 percent (%).
- 6. Has Body Mass Index range between 18 40.
- 7. Women of childbearing potential must have a negative serum pregnancy test at the Screening Visit and a negative urine pregnancy test at baseline before dosing.
- 8. Women of childbearing potential must use one of the following acceptable methods of contraception throughout the study (1 month prior to Screening through 1 month after last dose of study medication): oral contraceptive medication, intrauterine device (IUD), hormonal implants, injectable contraceptive medications, double-barrier methods, or tubal ligation.
- 9. Females who are postmenopausal (age-related amenorrhea ≥ 12 consecutive months and increased follicle-stimulating hormone [FSH] > 40 mIU/mL. If necessary, to confirm postmenopausal status, an FSH will be drawn at Screening) or who have undergone hysterectomy or bilateral oophorectomy are exempt from pregnancy testing.
- 10. Male patients must be willing to use acceptable contraceptive measures such as vasectomy or double barrier method and refrain from sexual activity with any

Version 3.0 33 of 85 20 April 2022

- female who is pregnant or lactating. Female partners of study participants are asked to use acceptable methods of contraception as listed in Inclusion #8 above.
- 11. Patient must be willing and able to swallow whole tablets.
- 12. Patient must be willing and able to comply with study procedures.

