9.2.3 Secondary Efficacy Analysis

This study will enroll gastroparesis patients with documented delayed gastric emptying and at least moderate symptom severity. The ANMS GCSI-DD scale will be used to assess the change from baseline in symptoms.

The ANMS GCSI-DD symptom assessments are based on a 24-hour recall period to minimize bias in patient recall. The ANMS GCSI-DD total gastroparesis symptom daily score is generated by summing the scores on each of the five symptom items (nausea, early satiety, postprandial fullness, upper abdominal pain, and number of vomiting episodes) and then dividing by 5, that is the number of items within the gastroparesis related symptom score. Thus, the maximum total symptom score could be (5 symptoms x maximum score 4 divided by 5); hence, the maximum score is 20/5=4. The ANMS GCSI-DD gastroparesis symptom daily score can range from 0 to 4. High scores on the ANMS GCSI-DD reflect greater symptom severity.

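### Do Sections 8.1.2 and 9.2.3 of the protocol define two different five-item totals for the ANMS GCSI-DD?

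*Combined protocol and SAP*

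**What the plan says.** Section 8.1.2 describes the diary in three steps.

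- It opens with "The instrument asks patients to rate the severity of five symptoms: bloating (feeling like you need to loosen your clothes), nausea" and continues with inability to finish a meal, excessive fullness and upper abdominal pain. Each is graded from 0 (none) to 4 (very severe).
- It then gives vomiting a separate rule: the daily number of episodes is used, "with the episodes capped at 4, so that the scoring is similar to the symptom severity scores of the other items".
- It defines the daily total as "summing the scores on each of the five symptom items and then dividing by 5, that is the number of items", without naming the items, and gives a maximum of 20/5 = 4.

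Section 9.2.3 repeats the formula and does name them: "five symptom items (nausea, early satiety, postprandial fullness, upper abdominal pain, and number of vomiting episodes) and then dividing by 5".

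The exploratory sub scores are listed at the end of 8.1.2 as "Change from baseline in the sub scores (nausea, early satiety, postprandial fullness, upper abdominal pain and number of vomiting episodes" and in the synopsis as "Change from baseline in the subscores (nausea, early satiety, postprandial fullness, upper abdominal pain and number of vomiting episodes". Table 2 in Section 3 gives the same five.

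Inclusion criterion 1 requires "Score of >2 on average of the screening days" (Section 5.1; the synopsis agrees) and cites neither scoring passage.

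**The concern.** A reader of 8.1.2 meets a list of five symptoms and, two paragraphs later, an instruction to sum five unnamed symptom items and divide by 5. The natural link is to the list just read, which contains bloating and not vomiting. Section 9.2.3 has the reverse. The stated maximum does not separate the two, because any five items scored 0 to 4 give 4.

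The score has two uses. It carries the four secondary endpoints, and it helps decide who is randomized. If the electronic diary computed the screening score with bloating while the analysis used vomiting, a patient could enter with a score above 2 and have an analysis baseline at or below 2, or be turned away when the analysis score would have qualified. With about 8 patients per arm, even one such patient is noticeable.

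**Working it through.** **Inputs.** Items scored 0 to 4, divisor 5, maximum 4 and a minimum clinically important difference of 0.50 (Section 8.1.2); item names (Sections 8.1.2 and 9.2.3); cut-off above 2 on the screening average (Section 5.1).

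**The plan's own figure.** Five items: 5 × 4 / 5 = 4, as stated, for either set. All six symptoms over 5: 6 × 4 / 5 = 4.8, outside the stated range of 0 to 4. So exactly one of the six named symptoms is outside the total.

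**Which one.** The passages side by side:

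| Place | Vomiting | Bloating |
|---|---|---|
| 8.1.2, symptoms graded for severity | not listed | listed |
| 8.1.2, vomiting rule | capped at 4 to match the other items | – |
| 8.1.2, total | items not named | items not named |
| 8.1.2, sub scores | listed | not listed |
| 9.2.3, total | listed | not listed |
| Synopsis and Table 2, sub scores | listed | not listed |

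The first row is the only one that favours bloating, and it concerns what is graded, not what is summed. Vomiting could not appear there, since it is counted. Capping it at 4 to put it on the scale of the other items has little purpose unless it is combined with them. No passage names a total that contains bloating.

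**Size of a misreading.** Let C be the screening average of the sum of the four shared items (0 to 16), and B and V the averages for bloating and vomiting.

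- Total with vomiting: (C + V)/5, above 2 when C + V > 10.
- Total with bloating: (C + B)/5, above 2 when C + B > 10.
- Difference: (B − V)/5, at most 4/5 = 0.8. This can exceed the 0.50 reference difference.
- If C ≤ 6, neither sum exceeds 6 + 4 = 10, so both fail. If C > 10, both pass. Eligibility can differ only for 6 < C ≤ 10, a four-item mean above 6/4 = 1.5 and up to 10/4 = 2.5.
- Within that band, the affected stretch of the four-item mean is |B − V|/4 wide: 0.25 for a gap of 1 point, 0.5 for 2, 0.75 for 3. It is zero when B = V.

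Example with C = 8 (all shared items at 2), B = 3, V = 0: (8 + 3)/5 = 2.2, which passes, against (8 + 0)/5 = 1.6, which fails.

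Across all 5^6 = 15,625 possible one-day item patterns, the two scores fall on different sides of 2 in 3,164 (20.2%). That counts patterns with equal weight. It is not an expected share of patients.

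**The case for a change.** The strongest case for a change is about timing. Section 9 of the protocol leaves technical detail to an analysis plan to be finalized before database lock, which is too late to correct decisions already taken at the randomization visit. Criterion 1 points to no formula, and 8.1.2, where someone setting up the diary would look first, does not list the scored items. The affected band also surrounds the cut-off, where borderline patients lie. A one-line clarification would cost almost nothing.

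Part of this stands. Section 8.1.2 does not name the five scored items and never says that bloating is collected but unscored, so a hurried reader could go wrong.

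The step from there to harm does not stand. It needs a diary programmed against the only itemized definition of the total, against the purpose of the vomiting cap and against the sub score list in the same section. The diary's scoring specification is not in the documents, so nothing shows that this happened or would. Criterion 1 refers to the score by name, and only one version of it is itemized.

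**Conclusion.** No change to the plan follows. This is a gap in one section that another section fills: 8.1.2 describes six symptoms collected, 9.2.3 names the five that are scored, and read together they give one total, usable for both eligibility and the secondary analysis. Repeating the 9.2.3 list in 8.1.2 would be tidier drafting but would alter no planned result.

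Even under the misreading, the effect is bounded: at most 0.8 points on the total, and a change of eligibility only in the band derived above. The GEBT half-time criterion and the investigator's three-month symptom criterion would still apply. The primary endpoint and the sample size do not use the score. A single reading applied to everyone before randomization would not favour any arm. Patients with an analysis baseline at or below 2 would stay in the Full Analysis Set, which is everyone randomized, and the secondary model takes the baseline value as a covariate.

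The conclusion assumes that the electronic diary and the analysis programs follow the itemized list in 9.2.3. The documents give no reason to think otherwise, but they do not show the diary specification either.

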1.2 Schedule of Activities (SoA)

 Table 1
 Schedule of Activities (SoA)

Procedure	Visit 1 (Screening)	Visit 2 (Screening) (Baseline)	Visit 3 (Randomization) Day 1	Visit 4 Day 7	Visit 5 Day 14	Visit 6 Day 28	Visit 7 48-72 hrs after Day 28 visit	Visit 8/ET Day 35
Visit Window	Days -	21 to -1		±2 days	+3 days	+1 day	_	±1 day
Informed consent	X							
Demographic information	X							
Medical history	X							
Inclusion/ Exclusion criteria	X	X	X					
Screening Lab testing (inc. Hep B/C, HIV and TB)	X							
Concomitant Medications	X	X	X	X	X	X		X
Vital signs	X	X	X	X		X		X
Physical exam ^g	X		X	X	X	X		X
¹³ C GEBT		X				X ^d		

Procedure	Visit 1 (Screening)	Visit 2 (Screening) (Baseline)	Visit 3 (Randomization) Day 1	Visit 4 Day 7	Visit 5 Day 14	Visit 6 Day 28	Visit 7 48-72 hrs after Day 28 visit	Visit 8/ET Day 35
Visit Window	Days -	21 to -1		±2 days	+3 days	+1 day		±1 day
ANMS GCSI-DD ^a		X	X	X	X	X		
Safety laboratory testing				X		X		X
Pregnancy test ^b	X		X	X	X	X		X
ECG ^h	X		Xi	X ^j	Xj	X		X e
C-SSRS	X		X	X	X	X		X
PGI-S			X			X		X
PGI-C			X			X		X
PAGI-SYM			X			X		
PAGI-QOL			X			X		
CGI-S			X			X		X
CGI-I			X			X		X
Adverse Events	X	X	X	X	X	X		X
Study Drug Dispensed			X	X	X	X		

Procedure	Visit 1 (Screening)	Visit 2 (Screening) (Baseline)	Visit 3 (Randomization) Day 1	Visit 4 Day 7	Visit 5 Day 14	Visit 6 Day 28	Visit 7 48-72 hrs after Day 28 visit	Visit 8/ET Day 35
Visit Window	Days -2	21 to -1		±2 days	+3 days	+1 day		±1 day
Study Drug Instructions	X	X	X					
Study Drug Administered			X			X ^c		
PK sample ^f			X			X	X^k	
Drug Accountability				X	X	X		

- a. ANMS GCSI-DD will be collected for 7 consecutive days after Screening Visit 2, but prior to randomization (i.e. from Days -7 to -1) as well as from Day 1 to Day 28.
- b. For WOCBP: Serum β-HCG at Screening Visit 1; Urine pregnancy test at subsequent visits
- c. Patients will take the dose of PCS12852 or placebo in clinic on Day 28.
- d. A blood glucose finger stick will be taken both before and at the completion of the GEBT.
- e. Repeat ECG at Visit 8, only if ECG at Visit 6 was abnormal.

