A second study, Study 102, evaluated the single and multiple dose PK and PD in healthy patients and in patients with functional constipation. This was a randomized, double-blind/open label, placebo/active controlled study. Prucalopride was the active control. An immediate release (IR) and a delayed release formulation (DR) of PCS12852 were studied over the 0.3 mg to 3 mg dose range for the IR and 0.5 mg to 2 mg for the DR. Systemic exposures following administration of the IR formulation increased linearly over the 0.3 mg to 3 mg dose range. Steady state concentrations were achieved by approximately Day 5, consistent with the half-life of approximately 24 hours. In the groups that evaluated the modified release formulation (DR), a delay in T_{max} for PCS12852 was noted, as expected. In terms of PD, PCS12852 resulted in pharmacologic activity related to stool assessments. There was a trend in improvement over placebo and comparable to prucalopride in terms of average weekly spontaneous bowel movements over the 2-week treatment period. PCS12852 was safe and generally well-tolerated with single and multiple doses under fasted and fed conditions in the healthy male and female patients and in patients with functional constipation.

In the 102 study, an exploratory evaluation was also performed to investigate the change from baseline in gastric emptying measured by GEBT on Day 7 (for the low dose-immediate release cohort (IRM) and the delayed release multiple dose cohort (DRM) only). The time for 10% and 50% gastric emptying was analyzed, along with the area under the curve (AUC) of the ¹³C rate measured in breaths and the analysis of the gastric emptying rate over time (45, 90, 120, 150, 180, and 240 minutes). In the IRM cohort, the change from baseline in gastric emptying rate increased in both PCS12852 IR 0.1 mg and 0.05 mg groups. Additionally, the AUC of the ¹³C rate showed a statistically significant change from baseline in the PCS12852 IR 0.1 mg group. Similar results were noted for DRM cohort.

All doses of PCS12852 in both of the clinical studies were well tolerated and no serious adverse events (SAEs) occurred. The most frequent treatment-emergent adverse events were diarrhea, headache, and nausea. There were no changes in vital signs, platelet aggregation or ECG parameters including no sign of QTc prolongation in time-matched ECGs monitored in the single ascending dose cohort.

Version 3.0 25 of 85 20 April 2022

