 To evaluate the effect of different doses of PCS12852 on the gastric emptying rate, as measured by the GEBT, in patients with moderate to severe idiopathic gastroparesis (IG) or DG To evaluate the PK profile of PCS12852 at different dose levels. 	 Change in gastric emptying rate from baseline as determined by the AUC of the gastric emptying rate over time as assessed by the GEBT at Visit 6 (Day 28) after administration of the PCS12852 or placebo. Change in gastric emptying rate from baseline using the t₁₀ and t₅₀ metric for gastric emptying rate. Concentrations of PCS12852 in plasma; PK parameters will be estimated from concentration-time data using noncompartmental methods, as data permit. 			
Secondary				
To evaluate the effects of different doses of PCS12852 on symptoms, as measured by the American Neurogastroenterology and Motility Society Gastroparesis Cardinal Symptom Index Daily Diary (ANMS GCSI-DD), in patients with moderate to severe idiopathic and diabetic gastroparesis	 Change from baseline in the ANMS GCSI-DD) (i.e., Day-7 to Day -1) (predose) and Day 7 (Day 1 to Day 7) Change from baseline in the ANMS GCSI-DD (i.e., Day-7 to Day -1) (predose) and Day 14 (Day 8 to Day 14) Change from baseline in the ANMS GCSI-DD (i.e., Day-7 to Day -1) (predose) and Day 21 (Day 15 to Day 21) Change from baseline in the ANMS GCSI-DD (i.e., Day-7 to Day -1) (predose) and Day 28 (Day 22 to Day 28) 			
To evaluate the effects of different doses of PCS12852 on symptoms or QOL, as measured by the PAGI-SYM, PAGI-QOL, PGI-S, PGI-C, CGI-S and CGI-I, in patients with moderate to severe idiopathic or diabetic gastroparesis	 Change from baseline in ANMS GCSI-DD score over time (Day 7, 14, 21, 28) by comparing Day 7 to Day 14, Day 14 to Day 21 and Day 21 to Day 28. Change from baseline in the sub scores (nausea, early satiety, postprandial fullness, upper abdominal pain and number of vomiting episodes) of the 			

Version 3.0 28 of 85 20 April 2022

Objectives	Endpoints
	ANMS-GCSI-DD over time (Day 7, 14, 21, 28) by comparing Day 7 to Day 14, Day 14 to Day 21 and Day 21 to Day 28.
	Change from baseline in PAGI-SYM and PAGI-QOL scores over time by comparing Day 1 to Day 28.
	Change from baseline in Clinical Global Impression-Severity (CGI-S) and Clinical Global Impression-Improvement (CGI-I) scores over time by comparing Day 1 to Day 28.
	Change from baseline in PGI-S and PGI-C scores over time by comparing Day 1 to Day 28.

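### The exploratory GCSI-DD subscore endpoint is labelled change from baseline, but the comparisons it names leave out the baseline week, so subscore change already reached in week 1 is not estimated

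*Combined protocol and SAP*

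**What the plan says.** Section 8.1.2 states that "The ANMS-GCSI-DD sub scores will also be assessed as an Exploratory Endpoint". The endpoint is then given as "Change from baseline in the sub scores (nausea, early satiety, postprandial fullness, upper abdominal pain and number of vomiting episodes") over time at Days 7, 14, 21 and 28, and is made operational "by comparing Day 7 to Day 14, Day 14 to Day 21 and Day 21 to Day 28". The exploratory endpoints in the Synopsis begin in the same way, "Change from baseline in the subscores (nausea, early satiety, postprandial fullness, upper abdominal pain and number of vomiting episodes"), and name the same three comparisons. Table 2 in Section 3 repeats them and uses the same form for the exploratory total score: "Change from baseline in ANMS GCSI-DD score over time (Day 7, 14, 21, 28) by comparing Day 7 to Day 14", and so on for the later weeks.

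The secondary total-score endpoints are built differently. Section 8.1.2 sets the baseline week against each treatment week, the first being "i.e. Day-7 to Day -1) (predose) and Day 7 (Day 1 to Day 7"), with matching entries for Days 8 to 14, 15 to 21 and 22 to 28. No section gives a comparison of that kind for a GCSI-DD subscore.

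The data for one exist. Footnote a of the Schedule of Activities has the diary completed over the baseline week and throughout treatment ("i.e. from Days -7 to -1) as well as from Day 1 to Day 28").

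Section 9.2.2 names an analysis model for the secondary endpoints. None is named for the exploratory GCSI-DD endpoints. Section 9 defers further detail to a SAP, and no separate SAP text accompanies the protocol.

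**The concern.** The label and the definition describe different quantities. The label promises change from the pre-treatment week at four time points. The definition lists three differences between consecutive treatment weeks. Whatever has changed between the baseline week and week 1 falls outside all three.

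An effect within week 1 is at least possible. Section 2.2 reports for Study 102 that "Steady state concentrations were achieved by approximately Day 5", which lies inside the first treatment week.

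At stake is how the trial reads individual symptoms. In a Phase 2a study the subscores would show whether nausea, satiety, fullness, pain or vomiting responds. If the listed comparisons are run as written, a symptom that improves early and stays improved could be reported as showing no change, and one that improves early and then relapses would be reported only as worsening.

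**Working it through.** The protocol gives no calculation for the subscores, so there is no figure of its own to reproduce. Its one power statement (Section 9.3) concerns the GEBT AUC and has no bearing here. The check is the algebra of the listed comparisons, followed by an illustration.

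**Notation.** Let B be the mean subscore over Days -7 to -1, and W1 to W4 the means over Days 1-7, 8-14, 15-21 and 22-28. Day 7 is read as the Day 1-7 mean, as Section 8.1.2 does for the total score.

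**Reading 1: the comparisons are the endpoint.** The quantities are W2 - W1, W3 - W2 and W4 - W3. B appears in none of them.

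**Reading 2: change from baseline is derived weekly, then compared between weeks.** The first comparison is (W2 - B) - (W1 - B) = W2 - W1. B cancels, and the other two reduce in the same way.

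On both readings the three comparisons add up to W4 - W1. The true week-4 change is W4 - B = (W4 - W1) + (W1 - B), so the missing part is exactly W1 - B, the change reached by week 1.

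**Illustration.** Inputs:
- A benefit of 0.50 points on one item. Section 8.1.2 gives 0.50 as the minimum important difference for the GCSI-DD score; applying it to an item is an assumption.
- Assumed time courses. The documents do not say when symptoms respond.

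Entries are differences from placebo. Randomisation makes the expected difference in B zero, so the second column is the true effect on change from baseline.

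| Assumed course | Effect on W1, W2, W3, W4 | Listed comparisons | Share of week-4 effect recovered |
|---|---|---|---|
| Full from Day 1, held | -0.50, -0.50, -0.50, -0.50 | 0, 0, 0 | 0% |
| Full from Day 5, held | -0.214, -0.50, -0.50, -0.50 | -0.286, 0, 0 | 0.286/0.50 = 57% |
| Even build-up by week | -0.125, -0.25, -0.375, -0.50 | -0.125 each | 0.375/0.50 = 75% |
| Daily linear growth to Day 28 | -0.071, -0.196, -0.321, -0.446 | -0.125 each | 0.375/0.446 = 84% |
| Full in week 1, then waning to zero at Day 28 | -0.50, -0.405, -0.238, -0.071 | +0.095, +0.167, +0.167 | sign reversed |

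For the Day 5 row, three of the seven days in week 1 carry the effect: W1 = -0.50 × 3/7 = -0.214, and W2 - W1 = -0.50 + 0.214 = -0.286. If Day 7 and Day 14 are instead taken as single diary days, this row also becomes 0, 0, 0.

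**Baseline as a covariate.** Adding B to the model does not recover the lost part, because randomisation balances B between arms and the outcome is still W2 - W1. A large simulation of the first row (20,000 per arm; assumed SDs of 0.7 between patients and 0.3 for weekly error) gave adjusted effects of -0.004, -0.001 and 0.000 on the three listed comparisons, against -0.501 on W1 - B and -0.506 on W4 - B.

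**The case against.** The strongest reply is that the wording is loose and the intention sound. The endpoint is called change from baseline and lists four time points, Day 7 among them. Purely week-to-week differences would give three values and would not need that label. On this view the four changes from baseline are the endpoint, and the comparisons are an added description. That intention is plausible, and a SAP could confirm it. But the only comparisons the text names leave baseline out, in the Synopsis, Table 2 and Section 8.1.2 alike. For PAGI-SYM and PAGI-QOL (Section 8.1.3.1), the same phrasing does name the contrast to be made, Day 1 against Day 28.

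A reader might infer more: that any benefit starting in week 1 is invisible on every subscore. The documents do not support that. A reading of zero needs the full effect to be present in the week-1 value and then to stay flat; the other rows of the table recover part of it. Steady state by about Day 5 was observed in healthy subjects and patients with functional constipation. It does not establish when gastroparesis symptoms respond.

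Nor would improvement across all the symptoms go unseen. By Section 9.2.3 the total score is the mean of the five items, so a 0.50-point gain on each is a 0.50-point gain in the total, which the secondary endpoints compare with baseline in all four weeks. What is at risk is attribution to individual diary items. PAGI-SYM (Section 9.2.4) offers related subscales, but it is a different instrument with a two-week recall and one Day 1 to Day 28 comparison, so it cannot locate a week-1 change.

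**Conclusion.** The point holds as a contradiction between label and definition in an exploratory endpoint. The algebra is exact: whichever way the listed comparisons are read, they omit W1 - B. The amount lost depends on the unknown time course. With an assumed 0.50-point item effect it runs from all of it (full from Day 1 and held), through 43% (full from Day 5, weekly means), to 25% or 16% (steady build-up by week or by day).

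The exploratory total score shares the wording but loses nothing in practice, because the secondary endpoints already use Days -7 to -1. The primary analysis, the secondary results, alpha and the sample size are unchanged. It would be too strong to say that the trial ignores the baseline diary or that no subscore change from baseline was intended; the supportable statement is that no subscore comparison with the baseline week is specified. Priority is minor.

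**What to change.** In the Synopsis, Table 2 and Section 8.1.2, define each subscore endpoint as the weekly mean (Days 1-7, 8-14, 15-21 and 22-28) minus the Day -7 to -1 mean, compared between arms as for the total score. Carry the same definition into the SAP before unblinding. Keep the week-to-week differences as descriptive summaries of time course, under a name that does not call them change from baseline.

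The cost is wording in three places and the SAP. No visit, diary entry or patient is added.
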